2. STUDY POPULATION

2.1. Population (base)

Patients indicated for elective AAA-surgery. We expect this selection of patients to be motivated to follow the training schedule.

2.2. Inclusion criteria

- Subjects with an AAA and an indication for elective operative repair.
- Informed consent.
- Fit for training as judged by the specialist in sports medicine and the cardiologist.
- More than 18 years of age.

2.3. Exclusion criteria

A potential subject who meets any of the following criteria will be excluded from participation in this study:

- Patients with an acute indication for surgery (symptomatic or ruptured AAAs)
- Patients with an indication for priority surgery (semi-elective; within three weeks):
 - o saccular aspect (16)
- Patients with tissue disorders (e.g. Marfan or other).
- Patients unfit for training (i.e. arrhythmogenic cardiomyopathy or electrical abnormalities of genetic origin (17))
- Patients unable to understand the objectives of this study.
- Patients unable to understand digital devices.

2.4. Sample size calculation

A multivariable regression analysis will be performed to identify important risk factors, such as a low fitness at the beginning of the training, a low or high BMI ($20 \ge BMI \ge 31$), and a low or high age ($50y \ge age \ge 90y$)(18). With the rule of thumb requiring 10 subjects per variable, and a chance of improvement of 50% (3 variables (fitness t= 0, BMI, and age) x 10 subjects x 0,5= 60); 60 patients will be required to include. Inclusion of one hundred patients will be necessary to perform a multivariable regression analysis with three variables, assuming an exclusion rate of 20%, and a drop-out rate of 20%. Three small sample, randomized controlled trials showed higher VO2 at VAT after 3, 6, or

9 weeks of training in gastroenterological cancer patients, patients with AAA, and rectal cancer patients, respectively: of 10,1%; 18%; or 29% (Table 1)(11, 19, 20).

Version number: 4

Study	Inclusion	n	Wks	% Impro-	VO2	SD	95%CI	VO2	SD	95%CI	ΔVO2
				vement	t=0			t=1			
Berkel(19)	GE-patients	28	3	10,1	9,6	1,2	9,1 - 10,1	10,5	1,36	10 - 11,1	0,9
Barakat(11)	AAA patients	20	6	18	12,2		10,5 - 14,9	14,4		12,3 - 15,4	2,2
Loughney(20)	Rectal CA	17	9	29	11,6	3,4	9,9 - 13,3	15	4,2	12,7 - 17,3	3,4
	total	65			•						

Table 1. Three randomized controlled trials evaluating fitness after training. Wks= weeks, SD= standard deviation, GE= gastroenterological, AAA= abdominal aorta aneurysm, and CA= cancer.

These patients reached an improvement ranging from 0.9 ml/kg/min up to 3.4 ml/kg/min (assumed mean 1.5 ml/kg/min). When subdividing the group of patients into a group with increased fitness (> 1.5 ml/kg/min) and a group without increased fitness (≤ 1.5 ml/kg/min), a dichotomous outcome is reached.

The multivariable analysis will be performed with other patient specific characteristics, as well, such as comorbidities. Modifiable factors will be analyzed as well, such as dietary habits, social economic status, frailty score, and other information collected in the questionnaires.

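### The cut-offs for low or high BMI and age in section 2.4 describe no possible patient and, read as 'or' and used as model groups, would leave too few patients to test age

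*Protocol*

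**What the plan says.** Protocol section 2.4 announces a multivariable regression and names the factors of interest: low fitness at the start, "a low or high BMI ($20 \ge BMI \ge 31$), and a low or high age ($50y \ge age \ge 90y". These brackets are the only place where the protocol attaches values to the BMI and age factors.

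The same section sizes the study on "3 variables (fitness t= 0, BMI, and age". It applies a rule of thumb ("With the rule of thumb requiring 10 subjects per variable") with "a chance of improvement of 50" per cent, and concludes that "60 patients will be required to include". After allowing 20% for exclusion and 20% for drop-out it states: "Inclusion of one hundred patients will be necessary to perform a multivariable regression analysis with three variables".

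The Introduction and Rationale names the same three factors without cut-offs. Section 8.1 plans a multivariable regression of improved against non-improved patients and does not say whether BMI and age enter as continuous or grouped variables. Section 2.2 limits age only to over 18 years. No expected age or BMI distribution appears anywhere.

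**The concern.** BMI and age are two of the three factors on which the primary objective rests, and the only definition attached to each is one that no patient can meet. An analyst who follows section 2.4 literally has two empty groups.

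Changing the symbols to an 'or' does not settle the matter. A split that sets patients aged 50 or younger, or 90 or older, against everyone else is likely to place almost all of an elective aneurysm-repair cohort on one side. A regression coefficient for such a factor is unstable or cannot be estimated, and a non-significant result would say nothing about whether age predicts response. For BMI, one indicator would treat very low and high BMI as a single category with a single effect.

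If the coding is left open until outcomes are known, it also invites a data-driven choice of cut-off in the primary analysis.

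**Working it through.** **1. The plan's own sample size.** Inputs from section 2.4: 3 variables, 10 per variable, 50% improving, 20% exclusion, 20% drop-out.
- Evaluable patients: 3 × 10 / 0.5 = 60, as stated. (The printed expression multiplies by 0.5, which would give 15; the result of 60 corresponds to division.)
- Included patients: 60 / (1 − 0.20 − 0.20) = 100, as stated. With the losses taken in sequence, 60 / (0.8 × 0.8) = 93.75, so 94.

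The 60 and 100 therefore reproduce for three one-parameter terms and do not depend on the cut-offs.

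**2. The inequalities as printed.** BMI must be ≤ 20 and ≥ 31 at once; age must be ≤ 50 and ≥ 90 at once. No number satisfies either.

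**3. Age, read as 'or'.** Assumption, because the protocol gives no distribution: normal, mean 70-75, SD 7-10. Extreme share p = Φ((50 − mean)/SD) + 1 − Φ((90 − mean)/SD); expected count = 60p; chance of an empty group = (1 − p)^60.

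| Mean | SD | ≤ 50 | ≥ 90 | p | Expected of 60 | Chance of none |
|---|---|---|---|---|---|---|
| 70 | 7 | 0.0021 | 0.0021 | 0.0043 | 0.26 | 77% |
| 74 | 8 | 0.0013 | 0.0228 | 0.0241 | 1.45 | 23% |
| 72 | 9 | 0.0073 | 0.0228 | 0.0300 | 1.80 | 16% |
| 70 | 10 | 0.0228 | 0.0228 | 0.0455 | 2.73 | 6% |
| 75 | 10 | 0.0062 | 0.0668 | 0.0730 | 4.38 | 1% |

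The expected count runs from about 0.3 to 4.4.

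**4. How many extreme-age patients a test would need.** Take 60 patients, 30 improved and 30 not, and the most favourable case: every extreme-age patient has the same outcome. Two-sided Fisher p by group size: 2 patients, 0.49; 3, 0.24; 4, 0.11; 5, 0.052; 6, 0.024. Six are needed, and the expected count is below six in every scenario. For an odds ratio of 3, approximate power with 1 to 3 patients in the group is 5% to 11%.

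**5. BMI, read as 'or'.** Assumption: normal, mean 26-28, SD 4-5. Same formula with 20 and 31.

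| Mean | SD | p | Expected of 60 | of whom ≤ 20 | of whom ≥ 31 |
|---|---|---|---|---|---|
| 26 | 4 | 0.1725 | 10.3 | 4.0 | 6.3 |
| 28 | 4 | 0.2494 | 15.0 | 1.4 | 13.6 |
| 26 | 5 | 0.2737 | 16.4 | 6.9 | 9.5 |
| 28 | 5 | 0.3291 | 19.7 | 3.3 | 16.5 |

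About 10 to 20 of 60 are in the pooled extreme group. With 12 to 18 in it, power for an odds ratio of 3 is about 36% to 47%, against 55% for an even 30/30 split. The factor is weakened but can be estimated. In each scenario the low tail is the smaller part (about 1 to 7 patients), so the pooled effect would mostly reflect high BMI.

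**6. Cost of further parameters under the plan's rule.** Each adds 10 / 0.5 = 20 evaluable patients: four parameters need 80, five need 100.

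**The case against.** The strongest reply is that the cut-offs are not a model specification. They appear once, as bracketed glosses in the sample-size section. Section 8.1 fixes no coding, and the count of one variable each for BMI and age suits continuous terms. Whether a predictor is continuous or grouped is commonly settled in a statistical analysis plan, which is not shown. The words before each bracket also make the 'or' meaning plain, so the symbols can be called a notation slip.

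Much of this stands. The near-empty age group is conditional on the cut-offs being used as model groups, and the counts rest on assumed distributions. It does not remove the point: section 2.4 names the regression and its factors and attaches impossible values to two of them. That is a wrong statement, not a detail left for later, and repairing the symbols alone leaves an unusable age grouping on the page.

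Two stronger readings are tempting and not supported:
- *Two of the three factors cannot be tested.* On the 'or' reading this applies to age only; BMI would have about 10 to 20 of 60 patients in its extreme group.
- *The study needs 100 evaluable patients, not 60.* Separate low and high indicators for BMI and age would give 1 + 2 + 2 = 5 parameters and 5 × 10 / 0.5 = 100. The protocol does not propose that model; it counts three variables, for which 60 and 100 reproduce.

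**Conclusion.** The definitions are wrong as written; this follows from the document alone and needs no assumption. On the evident 'or' reading, and only if the cut-offs become model groups, age would have about 0.3 to 4.4 of 60 patients in its extreme level (assumed mean 70-75, SD 7-10), against the 6 needed for significance under a perfect split. That is too few to test age. Under the same condition BMI remains testable (assumed mean 26-28, SD 4-5), with information lost and opposite extremes merged. The stated 60 evaluable and 100 included patients are not called into question by this point. The coding should be settled in the protocol before outcomes are examined.

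**What to change.** In section 2.4:
- Correct both inequalities so that each reads as 'at or below the lower value, or at or above the upper value'.
- State, there and in section 8.1, that age and BMI enter the primary regression as continuous linear terms, one parameter each. This matches the stated three variables and 60 evaluable patients.
- Say that the 20/31 and 50/90 cut-offs serve descriptive tables only.

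This costs a wording change, with no new data and no extra patients. The downside is that a linear term does not test the two-sided idea that both extremes behave differently from the middle. If that idea matters, prespecify a quadratic or spline term and count each added parameter: 20 more evaluable patients each under the plan's own rule, so 80 for one and 100 for two. With 60 evaluable patients, any such term should be labelled exploratory.

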6.3. Study procedures

Patients with an indication for AAA repair are routinely prepared for this operation with a visit at the anesthesiologist and the cardiologist. After the indication is set, the minimal waiting time for the operation is usually six weeks on average. This gives the

Version number: 4 21 of 41

subject the opportunity to start training. Surgery will not be postponed for this pilot study.

After the indication and informed consent, a questionnaire will be completed with the help of a professional research-nurse, and a cardiologic consultation will be performed. When subjects are fit for training, they will be informed about the use of the home-monitoring device. This will be followed by a visit at physical therapist (Figure 1).

Estimation of costs Aneurysm in motion					
	WZA (40	patients)	Treant (60 p	Totals	
Intake Luscii	€ 32	€ 1.280	€ 32	€ 1.920	€ 3.200
Alert Luscii	€ 14,70	€ 588	€ 14,70	€ 882	€ 1.470
Costs research bureau (30 minutes)	€ 20	€ 800	€ 20	€ 1.200	€ 2.000
	Totaal 1 jaar	€ 2.668		€ 4.002	
Both hospitals					€ 6.670

Table 2: Expected costs in participating hospitals, without insurance costs.

Following these three explanations (home monitoring, questionnaires, and training), the subject will be asked to start their home training during office hours, following a communication with the communication center of the home monitoring (Luscii). After each training and cooling down, parameters should be imported from the homemonitoring device and feedback will be given from the communication center. In case of anomalous measurements, the hospital will be contacted.

	Action	Conditions	Requirement Fit patients	Requirement Unfit patients
Inclusion criteria	Indication AAA repair	Elective repair	Eligible for inclusion	Eligible for inclusion
Inc	Informed consent	Signed	Eligible for inclusion	Eligible for inclusion
	Questionnaire	Various characteristics	One hour	One hour
	Specialist sports medicine	Consultation and CPET	One hour	-
	Cardiologist	Safe to perform training	Questionnaire and CPET	-
		Unsafe	-	Follow up
ıction	Explanation	Home monitoring device	One hour	-
Introduction	First visit physical therapist	At location physical therapist	One hour	-
iks	Daily training at home	Four days a week	Four hours	-
3-9 weeks	Weekly visit physical therapist	Once a week	One hour	-
Postop	Three months after the operation	Outpatient clinic	Ten minutes	Follow up

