9.2. Recruitment and consent

At the indication for AAA repair, patients will be informed by the treating vascular surgeon. Patients will receive an information document from their treating physician. Eligible subjects receive an appointment with the (co)investigator within one week. When they agree during an appointment with the (co)investigator, patients need to sign a declaration of informed consent. Eligible patients will be given a minimum of 24 hours, and a maximum of 2 weeks, to determine participation. When informed consent is signed, all subjects will complete the questionnaire and will perform a CPET. Bases upon the result of these tests the cardiac evaluation is made, if necessary complemented by other diagnostics. After training and during their surgery, patients will be followed until 30 days hereafter (Figure 1).

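### Section 2.4 prints a product that equals 15, not 60, and an assumed mean gain of 1.5 that Table 1 does not give; N is unchanged, but 10 patients per variable is not secured

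*Protocol*

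**What the plan says.** Section 2.4 of the protocol builds the sample size in three steps.

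- **Rule and share.** "With the rule of thumb requiring 10 subjects per variable, and a chance of improvement of 50" per cent are the two inputs, and the calculation is printed as "3 variables (fitness t= 0, BMI, and age) x 10 subjects x 0,5= 60); 60 patients will be required to include".
- **Inflation.** Enrolment is set at 100, "assuming an exclusion rate of 20%, and a drop-out rate of 20" per cent.
- **Outcome.** Table 1 lists three trials with mean gains in VO2 at VAT of 0.9 (n = 28, 3 weeks), 2.2 (n = 20, 6 weeks, AAA patients) and 3.4 (n = 17, 9 weeks) ml/kg/min. The text summarises them as "assumed mean 1.5 ml/kg/min" and splits patients into improved (above 1.5) and not improved (1.5 or below).

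The section ends by adding comorbidities to the multivariable analysis. It says that dietary habits, socio-economic status, frailty and other questionnaire items will be analysed as well. The primary objective is to identify three factors that predict response, and section 8.1 compares the two outcome groups by multivariable regression.

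**The concern.** This is the only justification given for the size of the primary analysis. Its printed equation is false, and its rule is worded in subjects, although the 60 arises only if the rule counts patients in an outcome group. Taken literally, 10 subjects per variable for three variables would ask for 30 patients.

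The second problem is the 50% share. The document offers no source for it. The cut-off is set equal to the assumed mean gain, and for a roughly symmetric change score that placement gives one half on each side. If the mean is not 1.5, the two groups are unequal and the smaller one limits how many predictors the model can carry.

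The plan has no slack. At exactly 50%, 60 analysed patients give 30 per group, which is 10 for each of three terms. Any imbalance in either direction, or any fourth term, takes it below its own rule. An overloaded logistic model gives unstable coefficients and overstated discrimination, which matters for a study meant to select patients for training.

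**Working it through.** **1. The plan's own figures**

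- As printed: 3 × 10 × 0.5 = 15. This is not 60.
- With division by the outcome share: 3 × 10 / 0.5 = 60. This matches.
- Enrolment with the two losses added: 60 / (1 − 0.20 − 0.20) = 60 / 0.60 = 100. This matches.
- Enrolment with the losses applied in sequence: 60 / (0.8 × 0.8) = 93.75, so 94. This does not match.

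The plan therefore used division and additive losses, and expects 60 analysed out of 100.

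**2. The mean of Table 1**

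- Weighted by n: (28 × 0.9 + 20 × 2.2 + 17 × 3.4) / 65 = (25.2 + 44.0 + 57.8) / 65 = 127.0 / 65 = 1.95.
- Simple: (0.9 + 2.2 + 3.4) / 3 = 6.5 / 3 = 2.17.
- Median, and also the AAA trial at six weeks: 2.2.
- Midpoint of the range: (0.9 + 3.4) / 2 = 2.15.

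None of these is 1.5.

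**3. Share improving and size of the smaller group**

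Assume a normal change score with mean m and standard deviation SD. The share improving is P = 1 − Φ((1.5 − m) / SD). The document does not give an SD of change, so 1.5 to 2.5 is assumed. The smaller group among 60 is 60 × min(P, 1 − P), and dividing by 3 gives patients per variable.

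| Mean gain | SD of change (assumed) | Share improving | Smaller group of 60 | Per variable |
|---|---|---|---|---|
| 1.5 (protocol) | any | 50% | 30 | 10.0 |
| 1.95 | 1.5 | 61.9% | 22.9 | 7.6 |
| 1.95 | 2.0 | 59.0% | 24.6 | 8.2 |
| 1.95 | 2.5 | 57.2% | 25.7 | 8.6 |
| 2.2 | 1.5 | 68.0% | 19.2 | 6.4 |
| 2.2 | 2.0 | 63.7% | 21.8 | 7.3 |
| 2.2 | 2.5 | 61.0% | 23.4 | 7.8 |

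The direction does not depend on the SD. With a symmetric change score, a mean above the cut-off always makes the non-improved group the smaller one. Only the size of the imbalance depends on the SD.

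**4. Number of terms, with no SD needed**

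- Three single-parameter terms at 50%: 3 × 10 / 0.5 = 60. All available patients are used.
- Four terms at 50%: 4 × 10 / 0.5 = 80 analysed, against 60 expected.

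Section 2.4 describes BMI and age as risk factors at both low and high values. If each were coded with two parameters, the three named variables alone would use five, and 5 × 10 / 0.5 = 100 analysed would be needed.

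**The case against.** **The sample size stands.** With the evident operator the plan reproduces 60 and then 100 exactly, and 60 patients at 50% deliver 10 per variable. This is correct. A reader might infer from the misprint that the true requirement is 15, or that the enrolled number is wrong. Neither follows.

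**The 50% may not depend on the 1.5.** Section 2.4 states the 50% before Table 1 and never says that it was derived from the assumed mean. Elsewhere the protocol uses 1.5 as the threshold for clear improvement in its own right. The link is an inference from the cut-off equalling the assumed mean and from the lack of any other basis.

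**A lower assumption could be defended.** The figure is labelled as assumed, and Table 1 mixes populations and durations. Its first two trials alone average 1.55, or 69.2 / 48 = 1.44 weighted. Inverse-variance pooling, with standard errors approximated from the printed SDs and intervals, gives about 1.1 under a fixed effect and 1.75 to 2.13 under random effects. A home-based programme might also achieve less than the supervised and in-hospital programmes named in the cited titles. The protocol gives none of these reasons, so the 1.5 is unexplained rather than shown to be false as a forecast.

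**Counting improved patients only** would give more than 10 per variable when more than half improve (60 × 0.572 / 3 = 11.4 up to 60 × 0.680 / 3 = 13.6). This does not help, because the rarer outcome limits the information in a binary model.

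**Shorter training.** Section 6.3 says "the minimal waiting time for the operation is usually six weeks on average" and that surgery is not postponed. Section 9.2 allows up to a week to the appointment and says "Eligible patients will be given a minimum of 24 hours, and a maximum of 2 weeks, to determine participation". A reader might infer that training will last only three to four weeks and that fewer than half will improve. The documents do not support this. The first phrase calls six weeks both a minimum and an average, the delays are maxima that cannot be subtracted from an average, and the two periods may overlap.

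**Conclusion.** Three statements hold without further assumptions. The printed equation is false. The assumed mean of 1.5 is not the mean of the table it summarises (1.95, 2.17, or 2.2 in the trial closest to this one). And 60 analysed patients at 50% leave no room for a fourth parameter, although the same section adds further characteristics to the multivariable analysis.

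The shortfall of 6.4–8.6 patients per variable is conditional. It rests on Table 1's means applying here, on an approximately normal change score, and on an assumed SD of change of 1.5 to 2.5. It is a sensitivity that the plan should show, not a demonstrated failure. Using 64 analysed patients, as sequential losses would give, moves the range only to 6.8–9.1.

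A reader might also conclude that the model must be cut to two predictors. That is not supported. At the low end, 19 of 60 is 9.5 per variable even for two, and the primary objective asks for three factors.

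**What to change.** Revise section 2.4, and section 8.1 to match.

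1. Print the calculation as 3 × 10 / 0.5 = 60, and state the rule as 10 patients in the smaller outcome group per model parameter. Show the enrolment step as 60 / (1 − 0.20 − 0.20) = 100.
2. Replace the assumed mean of 1.5 by a figure that Table 1 yields, or say why a lower gain is expected here. State the basis of the 50% separately from the choice of cut-off.
3. Give the share improving as a range with the SD of change assumed, and the resulting patients per parameter for 60 analysed.
4. Choose one primary model. Either keep a logistic model restricted to the three prespecified predictors, each coded with one parameter, and label all other characteristics exploratory. Or make the three-predictor primary model a linear regression of continuous change in VO2 at VAT, for which 60 patients give 60 / 3 = 20 per parameter and the split at 1.5 no longer limits the model.

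No extra enrolment, visits or measurements are needed. The cost is a text amendment and a less favourable stated number of patients per variable if the logistic model is kept. With the linear model, the improved versus non-improved comparison becomes a supporting description, so the wording of the primary objective would need to be aligned.

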Several trials have established exercise training to be safe in people with AAA and training does not seem to influence aneurysm growth (8-11). Professional supervision (e.g., physical therapy and in-hospital aerobic exercise training) is expensive. Home-based monitoring of exercising patients with AAA is less expensive, and device handling by patients has been positively evaluated before (12).

This study is designed to investigate whether patients with AAA can improve their preoperative aerobic fitness during 3- to 9-week (6 weeks on average) training program. It is primarily designed to evaluate which patients benefit most from this program, based on three outcome measures: initial fitness (CPET), BMI and age. Home training will be performed with home-monitoring and weekly support by a physical therapist.

A successful six-week training program is a true investment, and some patients will not be able to benefit from it. At this point we are unable to select patients who will benefit most. Improvement of aerobic fitness probably depends on a combination of patient specific factors, e.g., age and sex, comorbidity, aerobic fitness at the start of the training, dietary habits, comorbidity, SES, frailty index, ASA-score, physical strength, and the available social support. Training specific factors play a role as well, such as the number of prescribed training sessions, intensity, and the duration. This study is designed to select patients who will benefit most from training, based upon their initial fitness, their BMI and their age. Patients with an AAA and an indication for operative repair were often male smokers, with high blood pressure, and lipid profiles (1). Depending on their diligence, recruitment rate, adherence, completion, drop-out, and attrition rate, will be important. These rates will be evaluated in relation to SES and other characteristics. During training, patients will be supported with dietary substitutes, in order to maintain an anabolic condition (13). Due to the training at home, the Luscii app (CE-certificate 0476) enables patients to ask questions and this might stimulate them to start training, under the suggestion to be observed by the call center.

OBJECTIVES

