Primary Objective: To compare patient characteristics between patients with clear improvement (more than 1.5 ml/kg/min improvement in the VO2 at VAT) after a three-to-nine-week training program, with patient characteristics of those who do not improve after training We aim to identify three factors that predict responsiveness to improve preoperative aerobic fitness following the training program.

Secondary objective: To evaluate the preliminary effectiveness of an, on average, six-week home-monitored training program, in patients with AAA scheduled for elective AAA-repair to improve the preoperative VO2 at the ventilatory anaerobic threshold (VAT).

Other Secondary Objective(s):

Other secondary aims are to evaluate the feasibility of this three-to-nine-week homemonitored training program. A fall-out of some patients is expected because physical exercise requires perseverance and endeavor. This feasibility is evaluated with:

- recruitment rate (how many patients will consent to participate in relation to the patients refusing participation).
- adherence rate (how many patients will endure participation in relation to the patients who give up participation, a.k.a. dropout rate) (Appendix 1).
- completion rate (how many patients will complete participation in relation to the number of patients ending participation).
- drop-out rate (how many patients will drop out of participation in relation to the number of patients completing participation).
- Attrition rate (how many patients will ask if a transfer to another treatment facility is possible, a.k.a. churn rate).

Additionally, the individual (preliminary) effect of prehabilitation on other CPET variables will be evaluated, such as VO₂ at peak exercise (VO_{2peak}) and the oxygen uptake efficiency slope, individual response profiles on the progression in aerobic fitness, improvement of the steep ramp test throughout the program. (Appendix 2).

The postoperative course in patients after AAA repair will be described as well, by collecting data on the surgical intervention and postoperative outcomes (e.g., hospital length of stay (HLOS), number of complications, mortality rate, readmission rate).

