Following the explanation, patients have their intake with a physical therapist. The patients able to perform training, will be prescribed a personalized exercise program and will be followed by a local physical therapist. This includes a training scheme for exercises at home (Appendix 2). They will be asked to train at home and once a week at the physical therapist, check their vital sings with the pulse oximeter and de SMM, and communicate these vital

Version number: 4

signs with the Luscii app to a call center Altide. In case of previously set limitations, this call center will contact the hospital (Appendix 3).

Home-monitored training

All eligible patients will participate in a three-to-nine-week (average of six weeks), partly supervised, home-monitored training program prior to elective AAA-repair. The second CPET measurement is planned after the training program. Training frequency during the prehabilitation will be five sessions per week including a weekly evaluation by the physical therapist. Training sessions at home are prepared and should be able to be performed without extra adjuncts (see below). Before and after home-monitored training sessions without a physical therapist, subjects communicate oxygen saturation, heartrate, blood pressure, number of steps (nS), and number of smoked cigarettes through the Luscii app. According to these measurements, automatic advises will be given through the app (Appendix 3).

To evaluate a difference after the average of six weeks, subjects visit the specialist in sports medicine a second time to perform a CPET. Depending on the performance of patients in relation to the improvement in this second CPET, a subdivision of an improved and a stable (not improved) group will be made. It is expected that improved patients will show an increase of their VO2 at VAT of 1,5 ml/kg/min or more.

Three months after surgery, monitoring is complete, and preoperative patient characteristics of the groups will be compared.

Home-monitored exercises

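### Training runs for 3 to 9 weeks and the protocol says duration matters, yet one fixed 1.5 ml/kg/min cut-off defines improvement and no duration term is named for the primary model

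*Protocol*

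**What the plan says.** **Duration varies.** Section 1 (Home-monitored training): "All eligible patients will participate in a three-to-nine-week (average of six weeks), partly supervised, home-monitored training program prior to elective AAA-repair".

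**The surgical wait appears to limit it.** Section 6.3: "After the indication is set, the minimal waiting time for the operation is usually six weeks on average", and "Surgery will not be postponed for this pilot study".

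**The cut-off is the same for everyone.** The primary objective is "To compare patient characteristics between patients with clear improvement (more than 1.5 ml/kg/min improvement in the VO2 at VAT) after a three-to-nine-week training program", set against those who do not improve. Section 2.4 splits patients into "a group with increased fitness (> 1.5 ml/kg/min) and a group without increased fitness (≤ 1.5 ml/kg/min), a dichotomous outcome is reached".

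**Duration is named as a determinant.** The Introduction says: "Training specific factors play a role as well, such as the number of prescribed training sessions, intensity, and the duration". Section 2.4 then cites its evidence by duration, "Three small sample, randomized controlled trials showed higher VO2 at VAT after 3, 6, or" 9 weeks, and Table 1 gives gains of 0.9, 2.2 and 3.4 ml/kg/min respectively.

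**Duration is absent from the model as described.** The Introduction says: "This study is designed to select patients who will benefit most from training, based upon their initial fitness, their BMI and their age". Section 2.4 sizes the study on those three variables. The further covariates it mentions are patient characteristics, comorbidities and questionnaire items. Section 8.1 specifies a multivariable regression of improved against non-improved patients and names no training variable.

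**The concern.** The primary question is which patient characteristics go with response to training. The outcome is an absolute gain, measured after a period that may differ threefold between patients. If gain grows with weeks trained, two patients with the same capacity to respond can fall on opposite sides of 1.5 ml/kg/min because one trained for longer.

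There are two possible consequences:

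- If duration is unrelated to fitness, BMI and age, it adds unexplained variation to the classification and slightly weakens the three planned predictors.
- If duration is related to one of them, that predictor can pick up the effect of duration and be mistaken for a marker of responsiveness, or a real effect can be masked.

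The second route is plausible within this protocol. Section 1 (Recruitment) lets patients first judged unfit start training later if their condition improves, and Section 9.2 allows up to two weeks to decide on participation. With the surgery date unchanged, a late start can mean fewer training weeks. Patients who start unfit could then train for less time, while Section 6.1.1 expects those with poor fitness to benefit most. That is a possible mechanism; the protocol does not state it as a fact.

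**Working it through.** **1. The plan's own sample size.** Three variables, 10 subjects each, 50% improved: 3 × 10 / 0.5 = 60 evaluable. (Section 2.4 prints a multiplication, which would give 15; division is evidently meant.) With 20% excluded and 20% dropping out, added together: 60 / (1 − 0.20 − 0.20) = 100. Both figures reproduce, and neither allows for a duration term.

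**2. Inputs for the check.** Mean gains at 3, 6 and 9 weeks are 0.9, 2.2 and 3.4 (Table 1); the cut-off is 1.5 (Objectives, Section 2.4). The protocol gives no SD of individual change, so 2.0 is assumed, with a range of 1.5 to 2.5.

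**3. Chance of being classed improved.** P = 1 − Φ((1.5 − mean)/SD). For example, at 3 weeks with SD 2.0: 1 − Φ(0.6/2.0) = 38%.

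| Assumed SD | 3 weeks | 6 weeks | 9 weeks |
|---|---|---|---|
| 1.5 | 34% | 68% | 90% |
| 2.0 | 38% | 64% | 83% |
| 2.5 | 41% | 61% | 78% |

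**4. A weaker gradient.** The Table 1 means rise by (3.4 − 0.9)/(9 − 3) = 0.417 per week. With an assumed slope of 0.2 per week, a mean of 1.5 at six weeks and SD 2.0, the chances are 38%, 50% and 62%. With no slope, duration has no effect.

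**5. Share of variation due to duration.** If durations are spread evenly over 3 to 9 weeks, their variance is 6²/12 = 3. At 0.417 per week and SD 2.0, duration explains 0.417² × 3 / (0.417² × 3 + 2.0²) = 0.52/4.52 = 12% of the variance in change. At 0.36 per week it is 0.39/4.39 = 9%.

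**6. False positives for a predictor with no true effect.** Logistic model, 60 patients, SD 2.0, slope 0.417, durations spread evenly, 1,500 simulated trials per row:

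| Assumed correlation with duration | Duration omitted | Duration included |
|---|---|---|
| 0 | 4% | 5% |
| 0.3 | 9% | 6% |
| 0.5 | 15% | 4% |

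The Monte Carlo error on the 15% is about √(0.15 × 0.85/1500) = 0.9 percentage points. A repeat with another seed and 2,000 trials gave 9% and 18% for the two correlated cases, so the upper figure is approximate. At 0.2 per week the inflation is small: about 5 to 6% at a correlation of 0.3 and 7 to 9% at 0.5. With durations clustered around six weeks (assumed SD 1.25 weeks) and a slope of 0.36, it is about 6 to 7% and 9 to 10%.

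**7. Effect of a fourth term on size.** With 60 evaluable and 50% improved there are 30 events: 30/3 = 10 per variable now, 30/4 = 7.5 with duration added. Keeping 10 would need 4 × 10 / 0.5 = 80 evaluable and 80/0.6 = 133.3, so 134 included.

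**The case against.** **Table 1 is not a dose-response curve.** Its three trials (28, 20 and 17 patients) are in gastroenterological cancer, AAA and rectal cancer. Duration is wholly confounded with population and programme, and only the six-week trial is in AAA. This stands, so the percentages above are a rough guide. A straight line through the three means crosses 1.5 at about 4.4 weeks, but that figure should carry no weight.

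**Duration is unnamed rather than excluded.** Section 2.4 introduces its three factors as examples and promises further covariates, Section 6.2 ends its list open, and Section 8.1 lists none. The three variables are a sizing basis, not a closed model. This also stands. Even so, every addition named is a patient characteristic or questionnaire item, although the Introduction calls duration a determinant, and the sample size leaves no room for it at 10 per variable.

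**Bias needs a correlation that nobody has shown.** Correct. No section says that duration is related to age, BMI or fitness, and the 0.3 to 0.5 is assumed. Without it the false-positive rate stays near 5%.

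**The mixed model in Section 8.2 might cover it.** It does not. It belongs to the secondary analysis of change over time, not to the responder comparison.

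**Stronger readings that do not hold.** A reader might infer that waiting time largely decides who is a responder. At SD 2.0 with evenly spread durations it explains only about 9 to 12% of the variance in change. The 9- versus 3-week odds ratio, (0.829/0.171)/(0.382/0.618) = 7.8, compares only the two extremes. A reader might also infer that the wait dictates each patient's duration. That is a reasonable inference from Sections 1 and 6.3, but no sentence says it.

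**Conclusion.** The point holds in moderate form. The protocol names duration as a determinant, lets it vary threefold, applies one absolute cut-off and names no duration term for the primary analysis. Responder status will therefore partly reflect weeks trained, provided gain rises with duration in this population.

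The size is uncertain. Between 3 and 9 weeks the chance of being classed improved might run from 38% to 83% on the Table 1 means, or from 38% to 62% on the weaker assumed slope, both at an assumed SD of 2.0. The likely minimum harm is modest noise: losing 9 to 12% of the variance shrinks standardised effects by about 1 − √0.91 = 5% to 1 − √0.88 = 6%. False findings at roughly 9 to 15% arise only with a correlation of 0.3 to 0.5, the Table 1 slope and widely spread durations, and are less common otherwise.

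The study calls itself a pilot, and the covariate can be added before analysis if the dates are recorded. It is a recommended improvement, not a must-fix.

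**What to change.** In Sections 2.4 and 8.1, prespecify training duration as a covariate in the primary multivariable model: weeks from the start of training to the second CPET. Use the planned duration where it is available, because realised weeks can be influenced by how the patient fares during training. Report the effects of fitness, BMI and age at a common six weeks, for example as the predicted chance of improvement at that duration.

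Commit to recording the training start date and both CPET dates. The home diary in Appendix 1 has a date column, but no section lists these dates as study variables. Nor does any section say that planned duration is fixed at inclusion, and later starters may change it.

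The cost is one more parameter. Either state that events per variable fall from 10 to 7.5 with 60 evaluable patients, or raise the target to 80 evaluable (134 included) to keep the protocol's own rule. A cheaper complement at the planned 100 inclusions is a supporting analysis of change in VO2 at VAT as a continuous outcome with the same covariates. The 10-events rule does not bind there, and the dichotomous primary comparison stays in place. None of this alters the training schedule or the timing of surgery.
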